assent, the RA will conduct further screening for inclusion/exclusion criteria. *Baseline Visit:* At enrollment and prior to randomization, baseline measures in Table 3 will be obtained. Attendance will be recorded to assess effects of full vs. partial participation in FACE-Rare. *Follow-up Visit:* Blinded Assessor will obtain follow-up measures from families at 3-months post- intervention in person (clinic or home visit), by telephone or Telemedicine. See **Resources on Telemedicine**. **D.6.b. Measures**. Measures (**Table 2**) will be administered to the family by the blinded RA-Assessor. Investigators selected well-established measures with good reliability, validity, and normative data to increase replicability. Chart abstraction will be conducted by the blinded Assessor. A second blinded researcher will provide a validity *and* reliability check. Interrater reliability testing will be conducted. Rate differences will be reconciled by consensus, following well established procedures. ^{14,145} Disagreements will be resolved by the PI. See **Project Narrative** for questionnaire details.

Table 2: Measures	Method	Time	Description	
Primary Outcomes: *BL=Base	line *mo=mo	nth		
Beck Anxiety Inventory ¹⁴³	Survey	BL, 3 mo	QoL: emotional health. 21 items. Total Score will be used in analysis.	
FACIT-Spirituality-EX-Vs-4) ¹⁴⁴	Survey	BL, 3 mo	QoL : spiritual (meaning/purpose, peace). Is culturally sensitive to those with non-theistic beliefs. 23-items. Total Score will be used in analysis.	
Advance Care Document for Children with Rare Diseases ⁸⁴	Survey	3 mo	ACP Documentation in EHR & Decisional preferences- to continue all treatments; to continue all treatments with exceptions noted; to stop all treatments but comfort care.	
Standardized Data Abstraction Operationally defined ^{14,45,145} ,146	Chart Abstract	BL,3 mo or close-out	care prior to death, hospitalizations, Emergency Department visits, intensive care unit use,	
Moderators:				
Brief-Multidimensional Measure of Religion and Spirituality ^{62,63}	Survey	BL, 3 mo	Religious Coping : 5 items from our previous research: attend religious services, feel God's presence, pray privately, identify as religious, identify as spiritutal. 12,57,58	
Family Appraisal of Caregiving Questionnaire ¹⁴⁷	Survey	BL, 3 mo	Caregiver appraisal: caregiver strain, positive caregiving appraisals, caregiver distress, family well-being in past two weeks. 25 items.	
Time-Invariant Covariates:	•			

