AIM 1. To evaluate the initial efficacy of FACE-Rare in a pilot RCT on primary outcome: family QoL at 3-months post-intervention to seek effect sizes for a future fully powered R01. Hypotheses (H) 1a: FACE-Rare families will report significantly better QoL (emotional, spiritual) compared to controls. We will first describe the level of the outcome measures at both baseline and 3-month post-intervention by intervention group. Each group's preand post-intervention outcome levels at will be compared using paired t-test, respectively. Difference in change of each QoL measure from T₁ to T₂ between intervention groups will be examined using t-test. We will then apply the reliable change index (RCI)^{152,153} to assess how many individual patients in each intervention group would make a clinically significant amount of improvement in each of the QoL measures based on their RCI scores. The bias in outcome changes caused by measurement errors in the QoL scores will be taken into account in RCI. We will provide graphic portraval of individual outcome changes and RCIs by intervention group. An RCI of ±1.96 will serve as criteria for classifying the patients into categories of improved, unimproved, and deteriorated based on their QoL scores and RCIs. Those categories will be compared by intervention groups using two-sided Fisher's exact test. Based on our previous studies, we will assume a reliability of 0.80 for each of the QoL measure for conducting RCI. Because the focus on the individual rather than the group as a whole, data provided by the RCI allows the identification of individuals whose QoL measures have only changed marginally, or in an unusual direction, allowing the identification of subgroups for further analysis. The RCI thus also provides a systematic screening tool that has some advantages over the traditional visual inspection or setting cut-off points for inclusion based only on change relative to the group.

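### Change beyond ±1.96 on the RCI is labelled clinically significant with no clinical criterion, and one assumed reliability of 0.80 for both QoL scales leaves the category counts' calibration untested

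*Combined protocol and SAP*

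**What the plan says.** The text is in the combined protocol and SAP, D.9 Analytic Plan, Aim 1, H1a. After paired and two-sample t-tests, the plan applies the RCI to count how many people in each arm "would make a clinically significant amount of improvement in each of the QoL measures based on their RCI scores". The rule is numerical: "An RCI of ±1.96 will serve as criteria for classifying the patients into categories of improved, unimproved, and deteriorated". The input is a single figure: "we will assume a reliability of 0.80 for each of the QoL measure for conducting RCI". Its only stated basis is the team's previous studies. The arms are then compared: "Those categories will be compared by intervention groups using two-sided Fisher's exact test".

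Table 2 in D.6.b lists the two QoL scales. The Beck Anxiety Inventory is described as "QoL: emotional health. 21 items. Total Score will be used in analysis", and the FACIT spirituality scale as "23-items. Total Score will be used in analysis". On reliability, D.6.b says only this: "Investigators selected well-established measures with good reliability, validity, and normative data to increase replicability". No figure is given for either scale. The plan does not say whether 0.80 is internal consistency or test-retest reliability, or which standard deviation enters the index. It gives no clinical cut-off, normative range or minimal important difference.

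**The concern.** There are two separate problems.

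The first is the label. The RCI divides a person's change by the standard error of a difference between two fallible measurements. A value beyond 1.96 means the change is larger than measurement error would usually produce. It says nothing about whether the change matters to the caregiver. A report that follows the plan would state how many caregivers improved to a clinically significant degree on the primary outcome, with nothing in the method to support that statement.

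The second is calibration. Once the SD is set, reliability alone fixes the cut-off. A 21-item anxiety scale and a 23-item spirituality scale need not share one value. If a scale's true reliability is above 0.80, the fixed cut-off is too strict and real improvers are classed as unimproved. If it is below 0.80, measurement noise is counted as change. The plan has no sensitivity analysis that would show which counts depend on the assumed figure.

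**Working it through.** **Inputs from the documents.** Reliability is 0.80 for each scale and the cut-off is ±1.96 (D.9, H1a). Thirty dyads are randomized 1:1 with 15% attrition (D.9, Power & Sample Size Consideration).

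**Assumptions, not in the documents.** True reliabilities of 0.70 and 0.90; a baseline-to-3-month correlation of 0.6; mean shifts of 0.5, 0.8 and 1.0 baseline SD; two-sided alpha of 0.05 for Fisher's test.

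**The plan's own figure.** 30 × (1 − 0.15) = 25.5, which reproduces its 25–26 analysable dyads, or about 13 per arm.

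**Cut-off in SD units,** 1.96 × √(2(1 − r)):
- r = 0.70: 1.96 × √0.60 = 1.52
- r = 0.80 (as planned): 1.96 × √0.40 = 1.24
- r = 0.90: 1.96 × √0.20 = 0.88

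**False-change rate with the 0.80 cut-off and true reliability r,** 2 × [1 − Φ(1.96 × √(0.20/(1 − r)))]:
- r = 0.70: effective z = 1.60, rate 11.0%
- r = 0.80: effective z = 1.96, rate 5.0%
- r = 0.90: effective z = 2.77, rate 0.6%

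**Detection of a true 1 SD improvement at r = 0.90.** The error SD of a change is √0.20 = 0.447. With the 0.80 cut-off, 1 − Φ((1.24 − 1)/0.447) = 30%. With the cut-off for 0.90, 1 − Φ((0.88 − 1)/0.447) = 61%.

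**Fisher's test, improved versus not, 13 per arm.** With correlation 0.6 the SD of change is √(2 × 0.4) = 0.894. The control proportion improved is 1 − Φ(1.24/0.894) = 8%. In the intervention arm it is 1 − Φ((1.24 − shift)/0.894). Power comes from exact enumeration; the last two columns are the planned three-category test (also enumerated) and the planned t-test on change (noncentral t, 24 df).

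| Shift (SD) | Improved, FACE-Rare vs control | Fisher, improved vs not | Fisher, three categories | t-test on change |
|---|---|---|---|---|
| 0.5 | 20% vs 8% | 4% | 6% | 28% |
| 0.8 | 31% vs 8% | 16% | 20% | 59% |
| 1.0 | 39% vs 8% | 31% | 35% | 78% |

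With no shift, rejection is 0.2% for improved versus not and 1.6% for three categories, so the test is conservative. Over correlations of 0.5 to 0.8, power for improved versus not is 1–4% at 0.5 SD and 14–16% at 0.8 SD. The human-subjects section plans conservatively on 21 dyads; with 11 versus 10 and correlation 0.6, that power is 2% and 11%.

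**The case against.** The strongest reply is that nothing in the documents shows 0.80 to be wrong. It rests on earlier studies that the reader cannot see, and it may be right for one scale or both. That stands. A reader might infer that the counts will be miscalibrated, but the 11% and 0.6% are what-if figures in opposite directions, and the documents favour neither.

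A second reply is that replacing 0.80 with Cronbach's alpha from the sample could make matters worse. This also stands. Alpha measures internal consistency, whereas false change over three months depends on retest error. If alpha were 0.90 and retest reliability 0.80 (assumed), an alpha-based cut-off would call 2 × [1 − Φ(1.96 × √(0.10/0.20))] = 17% of unchanged caregivers changed, where the planned cut-off gives 5%. An alpha of 0.80 from 30 caregivers also has a 95% interval (Feldt) of about 0.68 to 0.89, nearly the whole range in doubt.

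A third reply is that the RCI is one of several H1a analyses. D.9 also plans a t-test on change and a covariate-adjusted model, takes the R01 effect size from the standardized mean difference, uses the RCI partly for graphs and screening, and concedes that power may be in question. This limits the consequence and keeps the point minor.

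A reader might also infer that Fisher's test should go. The documents do not support that: it is a valid small-sample test, and very large differences are detectable (70% versus 10% improved gives 88% power with 13 per arm).

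None of these replies answers the labelling problem, which does not depend on the true reliability.

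**Conclusion.** The point holds as a minor one, in two parts.

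The label is wrong as written. A ±1.96 rule alone cannot yield a count of clinically significant improvement, whatever the reliability. This part needs no assumption.

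The calibration part is conditional. The improved, unimproved and deteriorated counts could be off, with the false-change rate anywhere from 0.6% to 11% over assumed reliabilities of 0.90 to 0.70. The direction is unknown. It would be wrong to go further and say that the comparison between arms is biased towards a false positive: both arms share one cut-off, so a wrong reliability changes the counts and the power without inflating the type I error.

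On Fisher's test, the supported statement is limited. Under the assumptions above, its power for moderate shifts is low, so a non-significant result is not evidence of no difference.

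**What to change.** In D.9, H1a:

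1. Replace the clinical-significance wording with reliable change, unless a clinical criterion is added and applied alongside the RCI.
2. Keep 0.80 as the pre-specified primary value. State whether it is internal consistency or test-retest reliability, and which SD is used.
3. Repeat the three-way classification separately for each scale over a stated range, for example 0.70 to 0.90, and show how the counts move. Report the sample alpha as supporting information only.
4. Keep Fisher's test, and add a sentence that a non-significant result will not be read as no difference between arms.

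The cost is a little extra analysis on data already being collected, with no new visits or measures, and a less favourable label on the responder counts.

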D.8. Monitoring of Trial Conduct will be ongoing. D.8.a. Intervention Fidelity. Fidelity to CSNAT competency criteria will be accomplished during 3-day Protocol Training and monitoring by [name] in consultation with [name]. [name] and [name] will review all recordings of Session 3, Respecting Choices conversation to ensure intervention fidelity. D.8.b. Procedure Monitoring. [name] and [name] will monitor ongoing IRB compliance, documentation and preparation for annual continuing reviews. [name] and/or [name] will assure standardization of procedures, resolve any problems that are identified, confirm that all consents have occurred properly, and maintain participant and regulatory data D.8.c. Data quality monitoring. The REDCap database from previous FACE studies has been updated and expanded for this study. The system in place for data entry and implementation will be updated. See Resources for details. D.8.d. Safety Monitoring Committee (SMC) will meet twice yearly or more often as needed. See Data Safety and Monitoring Plan. The external SMC will be assembled by [name] and have the responsibility of reviewing safety information, study progress, and other relevant data. Duties will include review of any serious adverse event (SAE) or adverse event (AE), recommending follow-up or further action to the PI.

D.9. Analytic Plan. Various statistical methods, such as descriptive statistics, paired t-test, reliable change index (RCI), Fisher's exact test, and generalized estimating equation (GEE) models will be used to evaluate the proposed aims. All models will be estimated Bayesian approach. As such, data non-normality due to the small sample size can be handled in modeling under the assumption of missing at random (MAR). MAR is a plausible assumption that allows missingness to be dependent on observed measures (e.g., individual characteristics, intervention assignment, and/or baseline outcome measures).

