Finally, we will use GEE model to examine the intervention effect on QoL, controlling for covariates (due to the small sample size, only a few covariates-- age, gender, and race-- will be included). Bayesian approach that has superior performance in small samples without reliance on asymptotic and data normality assumptions will be used for model estimation. The goodness of fit of the model will be assessed by the posterior predictive checking. The goodness of fit of the model will be assessed by the posterior predictive checking. Statistical intervence interval of the difference between the observed and replicated model χ^2 values should center around zero, and the posterior predictive p-value (PPP) should be greater than 0.05. Statistical inferences will be made by examining the range of parameter estimates that captures 95% of the posterior probability distribution (i.e., 95% Bayesian credibility interval, CI). If the 95% CI of a slope coefficient estimate does not cover zero, then the coefficient is statistically significant at α =0.05 level. Mall models will be implemented using Mplus 8.3. The effect size of FACE-Rare intervention with respect to each specific outcome measure that will be used for our future R01 application will be estimated by the standardized outcome mean difference between intervention groups. The standardized slope coefficient of the intervention variable in a GEE model is the estimate of effect size, net of covariates.

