H3a: FACE-Rare families will have a significant higher probability of completing pediatric Advance Care Planning (pACP) documents for their child, compared to controls. Difference in the odds of completing pACP documents at 3-months post-intervention between intervention groups will be first examined using two-sided Fisher's exact test and then exact logistic regression)^{159,160} will be applied to examine the intervention effect on the odds of completing pACP, controlling for covariates (age, gender, race). H3b: FACE-Rare families will have a significant higher probability of having pACP documents locatable in the electronic health record, compared to controls. The analytical approaches proposed for testing H3a will be applied for testing H3b. Exploratory AIM. To evaluate the initial efficacy of FACE-Rare on child healthcare utilization (hospitalization, surgeries, and ER visits etc.), compared to controls. Previous studies suggest few cases in this brief time period, so descriptive statistics by intervention group without test will be reported with future plans to estimate costs associated with pACP. Power & Sample Size Consideration. Based on previous FACE research, 5,8,56 a sample size of 30 dyads will be sufficient to find statistically and clinically meaningful differences at 3 monthspost intervention and provide an effect size for a future R01. With attrition at 15%, 25-26 dyads will be available at 3-months post-intervention. With a small sample, the quality of the standard errors, parameter coverage, the power of detecting effects, and the quality of overall tests of fit may be in question. However, parameter estimates are often dependable even through sample size is small. Having realized the small sample size, we have proposed Fisher's exact tests, exact logistic regression, and particularly Bayesian for statistical tests and modeling. As such, the proposed study would provide useful information about the effect size that will be used to power a future R01. Investigators may not have sufficient power to report sex differences for caregivers. However, we will report our findings separately by sex in progress reports and publications. **D.10. Brief Timeline.** Investigators received IRB approval and completed the initial REDCap data base. Months 0-3: hire, train & certify project staff. Months 4-23: Ongoing recruitment, enrollment, assessments/data collection, fidelity monitoring, data cleaning. Months 23-24: Analysis and dissemination. See Study Timeline. **D.11. Alternative Strategies** We will only study staff willing to work flexible hours and to inconvenience themselves to meet families' scheduling needs. Weekly meetings will allow for early trouble shooting. If underenrolled, investigators will use CTSI-CN Power Trials to identify additional eligible children/families and/or add a study site. We will actively recruit fathers/male caregivers. See Recruitment and Retention Plan. Future Plans: If R21 aims are achieved, a future multi-site R01 will test the full theoretical model to improve pACP for children with rare diseases and their caregivers through family engaged pACP.¹⁶¹

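### The model for H1a to H1c is called a GEE but given Bayesian inference and MAR validity; as written it cannot be run, and the text does not say whether baseline QoL is in it

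*Combined protocol and SAP*

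**What the plan says.** The opening paragraph of D.9 (Analytic Plan) lists GEE among the methods and then states: "All models will be estimated Bayesian approach". It goes on to say that "data non-normality due to the small sample size can be handled in modeling under the assumption of missing at random (MAR"), and calls MAR plausible because missingness may depend on observed quantities. Baseline outcome measures are one of its examples.

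Under AIM 1 / H1a the plan says: "Finally, we will use GEE model to examine the intervention effect on QoL, controlling for covariates". The covariates are limited to age, gender and race because the sample is small. Estimation is Bayesian: "Bayesian approach that has superior performance in small samples without reliance on asymptotic and data normality assumptions will be used for model estimation". For fit, "The goodness of fit of the model will be assessed by the posterior predictive checking", using a replicated model chi-square and a posterior predictive p-value above 0.05. For inference: "If the 95% CI of a slope coefficient estimate does not cover zero, then the coefficient is statistically significant at α =0.05 level". The software is Mplus 8.3. The standardized GEE slope is the covariate-adjusted effect size for the R01.

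H1b adds an interaction to this GEE. H1c follows H1b, and H2 follows H1a.

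D.9 gives no likelihood, prior, working correlation or variance estimator. It does not say whether baseline QoL enters as a covariate, as a repeated outcome, or not at all.

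**The concern.** A GEE is a set of estimating equations. Without an added likelihood or pseudo-likelihood it has no posterior, no credibility interval and no replicated data for a predictive check, and the plan names none. The analyst must therefore drop one half of the specification, and the two halves behave differently in 21 to 30 families.

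Three properties that the plan relies on are then left without support:

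- **Error rate.** The 5% level is only the complement of the 95% interval. What is achieved depends on the unstated likelihood and prior, or on the unstated variance estimator.
- **Missing data.** An ordinary unweighted GEE is not valid under MAR in general. A likelihood model is, but only if it contains the variables that drive dropout.
- **Normality.** Freedom from normality cannot be claimed for a Bayesian model whose likelihood is not given. Non-normality and missing data are also separate problems: assuming MAR does nothing for the first, and a small sample does not cause it.

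At stake is mainly the adjusted effect size that this pilot is meant to hand to the R01.

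**Working it through.** **Inputs from the documents.** 30 dyads, 1:1, assessed at baseline and 3 months. Attrition is put at 15%: 30 × 0.85 = 25.5, which reproduces the 25-26 dyads in the Power section. The Human Subjects section works with 21 dyads. Earlier trials lost 5-7% (D.4). The nominal level is 1 − 0.95 = 0.05, which reproduces the stated α.

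**Inputs assumed.** Outcome SD 1; baseline to 3-month correlation r = 0.6 (range shown); dropout rules, priors and covariate distributions as given below.

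**1. Does leaving out baseline matter?** Suppose a fraction q of FACE-Rare families, those with the highest baseline anxiety, is lost and no controls are. The mean baseline of those who stay is −φ(z)/(1 − q), where z is the (1 − q) normal quantile. The bias in the 3-month difference is r times that.

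| q | φ(z) | φ(z)/(1 − q) | bias, r = 0.6 | bias, r = 0.3 to 0.7 |
|---|---|---|---|---|
| 5% | 0.1031 | 0.1086 | −0.07 SD | −0.03 to −0.08 |
| 7% | 0.1343 | 0.1444 | −0.09 SD | −0.04 to −0.10 |
| 15% | 0.2332 | 0.2743 | −0.16 SD | −0.08 to −0.19 |

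A large simulated sample at q = 15% and r = 0.6 gave −0.16 SD without baseline and 0.00 with baseline as a covariate. The cause is the omitted baseline, not the choice between GEE and Bayes: a Bayesian normal regression of the 3-month score on arm, age, gender and race carries the same bias.

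**2. If the Bayesian half is kept, what sets the error rate?** Simulation with no true effect: 15 per arm, two visits, no covariates, normal likelihood for both scores, mostly with baseline-dependent dropout.

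| prior on the arm effect | rejections at the nominal 5% |
|---|---|
| flat | 3.0-4.9% |
| sceptical, N(0, SD 0.5) | 0.7-2.1% |
| optimistic, N(0.5, SD 0.5) | 3.2-4.5% |
| tight optimistic, N(0.5, SD 0.25) | 26-36% |

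The N(0.5, SD 0.5) prior keeps the error rate, but moves the mean estimate to between 0.18 and 0.29 SD when the truth is zero. With a flat prior, bias stayed within about 0.01 SD for normal data.

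**3. If the GEE half is kept, what happens?** Fitting only the 3-month score on arm, age, gender and race (normal data, no effect, 20,000 runs per n), an uncorrected sandwich z-test rejected about 12%, 10% and 9% of the time at n = 21, 26 and 30. An ordinary t-test rejected about 5%. In the two-visit setting of step 2, uncorrected GEE rejected 6.5-8.1% with no dropout or completely random dropout. Under strong baseline-dependent dropout in opposite directions by arm, an exchangeable working correlation was nearly unbiased (about 0.02 SD) but rejected 6.9-9.7%. Independence was biased by −0.12 to −0.46 SD.

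**The case against.** The best defence is that GEE is simply the wrong label. The posterior, credibility interval, replicated chi-square and Mplus all point to a parametric Bayesian model, and the references include Bayesian analysis in Mplus and full-information estimation with incomplete data. On that reading MAR handling is available and a diffuse prior holds the error near or below 5%. I accept this as the likely intent. It does not supply the likelihood, the prior or the role of baseline.

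Four stronger readings are tempting, and the documents do not support them.

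- *The error rate and MAR protection do not exist.* They are not established by the text, which is a weaker statement. A sensible completion of the plan would provide both.
- *The trial will run at 9-12% false positives.* That holds only for an uncorrected sandwich z-test. The plan specifies neither that variance nor that test.
- *This model alone decides H1a.* D.9 also plans a between-arm t-test on change and Fisher's test on reliable-change categories. The GEE/Bayes mismatch touches neither.
- *Bayesian estimation of all models contradicts H3.* H3a specifies Fisher's test and "then exact logistic regression", and the Power section lists exact and Bayesian methods side by side. The specific text governs; this is a drafting slip.

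The dropout illustration is also severe. It is one-sided and deterministic, whereas D.4 reports no significant differential attrition in earlier trials with a usual-care control. Even 0.16 SD is under half the unadjusted standard error at n = 26, √(1/13 + 1/13) = 0.39 SD. The plan itself concedes that standard errors and coverage may be in question. These points limit the size of the problem. They do not make the specification runnable. Part of the H1a text is garbled by PDF reading, but the sentences quoted here are intact.

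**Conclusion.** The specification for H1a, carried into H1b and H1c, is wrong as written: a method without a likelihood is given likelihood-based inference, fit checks and missing-data validity. The 5% level and the MAR protection are therefore not established.

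On the likely intended reading, the substantive gap is that the MAR justification cites baseline outcomes while the listed covariates omit them. If baseline is left out, the R01 effect size could be off by about 0.16 SD in the illustrated case (r = 0.6, top 15% of one arm lost) and by 0.07-0.09 SD at 5-7% attrition. If baseline is already modelled as a repeated outcome in a likelihood model, that bias is about zero. The text does not say which applies. The correlation, dropout rules and priors are my assumptions, not figures from the plan.

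This should be fixed. In a pilot seeking effect sizes, with separate t-tests planned, it does not invalidate the trial.

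**What to change.** Replace GEE in D.9 (opening paragraph, H1a, H1b, and by reference H1c) with one Bayesian likelihood model. Model the baseline and 3-month scores jointly, or the 3-month score adjusted for baseline, with arm, age, gender and race. State the likelihood and weakly informative priors, and define the effect size as the standardized arm effect at 3 months from that model. Delete the sentence that has MAR deal with non-normality, and the claim of no reliance on normality; add a Student-t sensitivity analysis. Limit the sentence on Bayesian estimation to these models, so that the t-tests and exact methods are clearly outside it.

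If GEE is preferred, include baseline, state the working correlation, use small-sample-corrected standard errors with a t reference, and delete the posterior predictive and credibility-interval text. MAR should then be claimed only if a weighting or imputation method supports it.

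The cost is SAP wording, settled before analysis. Both QoL scores are already collected at baseline. Intervals will be wider than those of an uncorrected GEE, and the baseline term uses one more parameter in a small sample.

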H1b. Family caregiving appraisals will moderate effect of FACE-Rare on QoL outcomes. The interaction between a caregiving appraisal variable and intervention will be included in the GEE model described above to examine whether and how the intervention effect on QoL measures would be moderated by the family caregiving appraisal. If the interaction is statistically significant, we would conclude the intervention effect on the outcome depends upon the value of the caregiving appraisal. A positive coefficient (e.g., 0.2) of the interaction indicates that intervention effect would increase the magnitude of this coefficient (e.g., 0.2), corresponding to one unit increase in the caregiving appraisal score. Each appraisal measure will be recoded as the deviation from its grand mean so that the recoded appraisal measure has a meaningful 0 that represents the mean level of the appraisal in the sample. As such, the main effect of intervention is interpreted as the intervention effect corresponding to the mean level of the original appraisal measure (i.e., the 0 of the recoded appraisal measure). When the interaction effect is statistically significant, the corresponding main effect, no matter it is statistically significant or not, must remain in the model and be included in calculation of intervention effect.

Testing H1c. Religiousness will moderate the effect of FACE Rare on QoL outcomes. The same analytical approaches proposed for testing H1b will be applied to test **H1c**.

AIM 2. To evaluate the effect of FACE-Rare on satisfaction with study participation.

H2: FACE-Rare families will report significantly greater satisfaction, compared to controls. The same analytical approaches proposed for testing **H1a** will be applied to test **H2**.

AIM 3. To evaluate the initial efficacy of FACE-Rare on secondary outcomes: plans and actions: completion of and documentation of advance care plans in the electronic health record at 3-months post-intervention.

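### H1b and H1c conclude moderation from any interaction significant at 0.05, across 10 or more unadjusted tests: roughly a 30-40% chance of at least one false moderator if none exists

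*Combined protocol and SAP*

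**What the plan says.** The moderation hypotheses belong to Aim 1. In D.9, under H1b, an appraisal-by-intervention interaction is added to the outcome model, each appraisal measure is centred on its own mean, and the result is read by this rule: "If the interaction is statistically significant, we would conclude the intervention effect on the outcome depends upon the value of the caregiving appraisal".

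The threshold comes from the H1a text in D.9. If the 95% credibility interval of a coefficient excludes zero, "then the coefficient is statistically significant at α =0.05 level". Religiousness (H1c in D.9, numbered H2c in the Specific Aims) inherits the rule: "The same analytical approaches proposed for testing H1b will be applied to test" H1c.

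Table 2 (D.6.b) gives the pieces from which the tests are built:

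- Two QoL outcomes, each a single score: the Beck Anxiety Inventory ("QoL: emotional health. 21 items. Total Score will be used in analysis") and the FACIT spirituality scale ("23-items. Total Score will be used in analysis").
- Four appraisal dimensions: "caregiver strain, positive caregiving appraisals, caregiver distress, family well-being in past two weeks".
- Five religion items, with no scoring rule.

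No section names a primary moderator, an omnibus test or a multiplicity adjustment. The healthcare-utilization aim is labelled exploratory and is reported descriptively without testing. H1b and H1c receive neither treatment.

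**The concern.** The rule turns each significant coefficient into a substantive conclusion, and it is applied to many coefficients. The error rate that matters to a reader of the results is the chance that the trial names at least one moderator when there is none. At 0.05 per test with no adjustment, that chance is several times 5%.

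A named moderator has uses beyond this trial. Section A.1 says that findings may inform interventions directed at religious beliefs and practices linked to poorer QoL, and D.11 plans a later multi-site trial of the full theoretical model. A chance interaction could feed either one.

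The power paragraph in D.9 concedes that standard errors and power may be doubtful at this sample size. It says nothing about false positives. The exact and Bayesian methods that it offers in response do not address multiplicity.

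**Working it through.** **Sample size.** D.9 expects 25-26 dyads after 15% attrition from 30 randomized: 30 × (1 − 0.15) = 25.5, which reproduces. The Human Subjects section instead plans on 21 dyads (21/30 = 70% retained). Both were tried. The plan states no effect size, SD or power for interactions, so there is no power figure to reproduce.

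**Number of tests.**

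- H1b: 4 appraisal dimensions × 2 QoL totals = 8.
- H1c, one composite: 1 × 2 = 2, total 10.
- H1c, five items singly: 5 × 2 = 10, total 18.

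The counts are inferred from Table 2. Both moderator questionnaires are collected at baseline and at 3 months, and D.9 does not say which values enter the model. Using both would add tests.

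**False-positive chance, independent tests.** 1 − 0.95^k:

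- k = 8: 34%
- k = 10: 40%, with 10 × 0.05 = 0.5 false positives expected
- k = 18: 60%, with 18 × 0.05 = 0.9 expected

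**False-positive chance, correlated tests.** Simulated trials with no interaction, 3,000 per setting, n = 26. Each outcome was regressed by least squares on arm, three covariates, one centred moderator and its product with arm, with two-sided t tests at 0.05. The correlations are assumptions.

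| Correlation: appraisals / religion items / outcomes / across the two sets | 10 tests | 18 tests |
|---|---|---|
| 0 / 0 / 0 / 0 | 42% | 59% |
| 0.3 / 0.4 / 0.3 / 0.1 | 38% | 57% |
| 0.5 / 0.6 / 0.5 / 0.2 | 34% | 49% |
| 0.7 / 0.8 / 0.7 / 0.4 | 27% | 38% |

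A second simulation (n = 26, outcome correlation 0.4, moderator correlation 0 to 0.7) gave 29-37% for 10 tests and 39-60% for 18. At n = 21 the first simulation gave 28-41% and 37-60%, so the sample size hardly affects this error.

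**Power at a single test.** Assume 13 per arm, residual SD 0.8-1.0 in units of the QoL SD, the moderator scaled to SD 1, and 21 degrees of freedom (26 minus intercept, arm, moderator, interaction and baseline).

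- SE of the slope difference = residual SD × √(1/12 + 1/12) = residual SD × 0.408
- Detectable at 80% power = SE × (2.080 + 0.859) = SE × 2.939
- Residual SD 0.8: 0.327 × 2.939 = 0.96
- Residual SD 1.0: 0.408 × 2.939 = 1.20

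By the same formula, a slope difference of 0.7 has 37-53% power and one of 0.5 has about 21-31%.

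**The case against.** **This is a pilot seeking effect sizes.** True, and it lowers the stakes. It does not remove a sentence that says what would be concluded. If effect sizes are the purpose, the sentence is not needed.

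**The model is Bayesian.** An informative shrinkage prior could reduce the error. None is given, and D.9 itself equates its interval rule with a 0.05 level. The simulated figures remain a stand-in for the planned model.

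**H1b and H1c are separate hypotheses, so pooling them is a choice.** This is fair. In a further null simulation with a composite religion score, H1c alone gave 7-9% and H1b alone 22-33%. H1b is inflated by itself; H1c on one composite is inflated much less.

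**The 18-test count is not in the plan.** It stands only as an upper bound. H1c speaks of religiousness in the singular, and an unstated scoring rule is a gap, not a plan for ten tests.

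**Moderation by religiousness has support from earlier work.** Section A.1 reports it, so a state in which nothing moderates is the least favourable case for H1c. That does not help the eight appraisal tests.

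Three stronger readings are tempting and are not supported:

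- That a false moderator claim is likely. The chance passes 50% only with single-item religion tests and low correlation.
- That the rule is more apt to name a false moderator than to detect a real one. This sets an error rate over many tests against the power of one test. It also fails on the numbers: at a slope difference of 0.7, power of 37-53% is not generally below the 10-test error rate.
- That the small sample causes the false positives. Results at 21 and 26 families nearly agree; small numbers lower power, which is a separate weakness.

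**Conclusion.** The concern holds in this form. As written, the H1b/H1c rule carries roughly a 30-40% chance of at least one false moderator conclusion with 10 tests when nothing moderates the effect (27-42% over all the correlations tried). It rises to about 60% only if the five religion items are tested one by one and are weakly correlated. Across these settings the chance is about 5 to 12 times the nominal 5%.

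The defect lies in the stated rule combined with the per-coefficient threshold. The size rests on the inferred test count, the assumed correlations and least squares in place of a Bayesian model with an unstated prior.

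Separately, about 26 families give 80% power at one test only for interactions of about 1.0-1.2 SD of QoL per SD of moderator, assuming residual SD 0.8-1.0. A significant interaction would therefore be weak evidence of moderation.

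**What to change.** In D.9:

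1. Replace the sentence that draws a conclusion from a significant interaction. State that H1b and H1c are exploratory and that this pilot will draw no conclusion of moderation.
2. Report every interaction estimate with its 95% credibility interval, and state how many interactions were examined.
3. Name one prespecified religiousness score, and state whether baseline or 3-month moderator values are used.

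The same label should appear beside the hypotheses in the Specific Aims.

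The cost is wording, plus a confirmatory moderation claim that the pilot gives up. No extra families or data are needed, and the effect-size purpose is kept. Keeping the tests with a Bonferroni adjustment would cost more. For a large interaction (assumed f² = 0.35, n = 26, 7 model parameters), power falls from 82% at 0.05 to 46% at 0.05/10 = 0.005, and to 37% at 0.05/18 = 0.0028.
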